9.4 Discharge

- Upon discharge from the hospital, the nurse will log patient out of the Palarum PUP™ System. The PUP™ socks will be placed in the Palarum laundry receptacles located on each hospital floor.

10 ADVERSE EXPERIENCE REPORTING AND DOCUMENTATION

10.1 Adverse Events

An Adverse Event has to meet three basic criteria to be reportable; an AE has occurred, the device is associated with the AE and the AE led to 1 of 4 outcomes: decline in state of health of patient, threat to public health, could lead to death or serious injury if it occurs.

The Investigator will probe, via discussion with the subject, for the occurrence of AEs during each subject visit and record the information in the site's source documents.

Adverse events will be recorded in the patient CRF. Adverse events will be described by duration (start and stop dates and times), severity, outcome, treatment and relation to study, or if unrelated, the cause.

10.2 Serious Adverse Experience Reporting

Study sites will document all SAEs that occur (whether or not related to study protocol) per UCSF CHR Guidelines. The collection period for all SAEs will begin after informed consent is obtained and end after procedures for the final study visit has been completed.

In accordance with the standard operating procedures and policies of the local Institutional Review Board (IRB)/Independent Ethics Committee (IEC), and OSU's CH Guidelines, the site investigator will report SAEs to the IRB/IEC.

10.3 Medical Monitoring

Medical monitoring will be provided by the research team. If further medical assistance is determined necessary, then medical assistance will occur through standard of care per OSU Brain and Spine Hospital standard operating processing.

11 DISCONTINUATION AND REPLACEMENT OF SUBJECTS

11.1 Early Discontinuation of Study

A subject may be discontinued from study treatment at any time if the subject, the LAR, the investigator, or the Sponsor feels that it is not in the subject's best interest to continue. The following is a list of possible reasons for study treatment discontinuation.

- Subject or LAR withdrawal of consent
- Subject is not compliant with study procedures including but not limited to intermittent wearing of the sock, refusal after enrollment to wear the socks, or repeatedly engaging in activity which defeats the integrity of the electronic circuitry of the sock.
- Adverse event that in the opinion of the investigator would be in the best interest of the subject to discontinue study treatment
- Protocol violation requiring discontinuation of study treatment
- Sponsor request for early termination of study
- All subjects are free to withdraw from participation at any time, for any reason, specified or unspecified, and without prejudice.
- Reasonable attempts will be made by the investigator to provide a reason for subject withdrawals. The reason for the subject's withdrawal from the study will be specified in the subject's source documents. Refer to Section 10 for early termination procedures.

11.2 Withdrawal of Subjects from the Study

- A subject may be withdrawn from the study at any time if the subject, the investigator, or the Sponsor feels that it is not in the subject's best interest to continue.
- All subjects are free to withdraw from participation at any time, for any reason, specified or unspecified, and without prejudice.
- Reasonable attempts will be made by the investigator to provide a reason for subject withdrawals.
 - The reason for the subject's withdrawal from the study will be specified in the subject's source documents.
 - As noted above, subjects who discontinue study treatment early should have an early discontinuation visit. Refer to Section 10 for early termination procedures.

12 PROTOCOL VIOLATIONS

- A protocol violation occurs when the subject or investigator fails to adhere to significant protocol requirements affecting the inclusion, exclusion, subject safety and

primary endpoint criteria. Protocol violations for this study include, but are not limited to, the following:

- Failure to meet inclusion/exclusion criteria
- Failure to comply with Good Clinical Practice (GCP) guidelines will also result in a protocol violation. The Sponsor will determine if a protocol violation will result in withdrawal of a subject.
- When a protocol violation occurs, it will be discussed with the investigator and a Protocol Violation Form detailing the violation will be generated. This form will be signed by a Sponsor representative and the Investigator. A copy of the form will be filed in the site's regulatory binder and in the Sponsor's files.

13 STATISTICAL METHODS AND CONSIDERATIONS

Prior to the analysis of the final study data, a detailed Statistical Analysis Plan (SAP) will be written describing all analyses that will be performed. The SAP will contain any modifications to the analysis plan described below.

13.1 Demographic and Baseline Characteristics

Demographic and baseline characteristics will be summarized using appropriate descriptive statistics including the mean and standard deviation for continuous values and counts and proportions for discrete variables.

13.2 Analysis of Primary Endpoint

The primary endpoint for this study is the number of patient falls. This will be expressed as a rate per patient days where patient days are counted from the initiations of the PUP™ System until discharge or removal from the fall risk protocol. Using a one-sided one-sample test for Poisson means, we will test whether the observed fall rate is less than the historical rate of 0.004. This test will be conducted at the alpha=0.1 level. Results will be presented as the fall rate and the corresponding one-sided 90% confidence interval which will provide an upper bound for the fall rate.

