HIPAA	Health Insurance Portability and Accountability Act of 1996
HUC	Health Pod Coordinator/UCA Monitor
ICF	Informed Consent Form
IEC	Independent Ethics Committee
IRB	Institutional Review Board
IRL	In Room Locator
IRT	In Room Tablet
PI	Principal Investigator
PLS	Palarum Local Server
PUP™	Patient is Up Fall Prevention System
RSSI	Receive Signal Strength Indicator
RTLS	Real Time Location System
PCS	Palarum Cloud Service
SAE	Serious Adverse Experience
WIRB	Western Institutional Review Board

PROTOCOL SYNOPSIS

TITLE	Testing the Effectiveness of a Fall Prevention System
SPONSOR	[name] PhD
FUNDING ORGANIZATION	Palarum, LLC
NUMBER OF SITES	1 Site on 3 floors of the Ohio State University Wexner Center Brain and Spine Hospital; (8 South, 9 South, 10 South, 8 East, 9 East & 10 East)
RATIONALE	
Each year, between 700,000 and 1,000,000 people in the United States fall in a healthcare environment (Agency for Healthcare Research and Quality, 2015). Falls can have a widespread and significant impact on health, can be deadly, and often result in high costs. Falls with serious injury are consistently among the Top 10 sentinel events reported to The Joint Commission's Sentinel Event database (The Joint Commission, 2015). The average 200-bed hospital might log 300 patient falls a year (based on 5 patient falls per 1000 patient days), which results in \$10,200 per fall in medical costs annually – or more than \$3 million. (Agency for Healthcare Research and Quality)
 
The best way to reduce the number of falls is to prevent them. A whole marketplace of bed and chair alerts and other devices has been developed to address the need, yet the numbers increase. On a busy patient floor, nurses lose valuable seconds just figuring out which patient's bed alert is sounding. We expect research to show that the Palarum PUP™ System reduces the incidence of falls.

STUDY DESIGN	Single arm trial
PRIMARY OBJECTIVE	To determine if the fall rate (as measured by falls per 1000 patient days) for patients designated “fall risk” decreases with the use of the intervention (Patient is UP fall prevention technology [PUP™]) when compared to historical NDNQI data for the prior 12 months (“Benchmark Data”) from nursing units where the intervention is being undertaken.

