	
Android tablet (IRT), a nurse station Android monitor (HUC), a local server (PLS), a cloud server (PCS), a Bluetooth Low Energy beacon(s), an Android smart notification device, and an e-textile sock connected sensor transmitter (PUP™ sock).
 
The PUP™ sock monitors and transmits pressure, force, acceleration and motion data to IRT and PLS, and HUC and PCS. This data is evaluated and validated by an Android application on the IRT to determine whether or not a fall risk patient is standing unaccompanied by a caregiver. If a monitored patient is standing unattended, the PLS locates and alerts the Smart Notification Devices of the five (5) closest healthcare providers and the HUC using the beacon technology.
 
Alerts are terminated by the Smart Notification Device and PLS based on caregiver proximity to the patient. All data, alerts, suspensions, terminations and notifications are recorded by the PCS. On a daily basis, PCS reports are produced which contain data for each patient enrolled, number of alerts, excessive alerts, and caregiver response time, as well as summaries by Pod and entire facility.
 
All Brain and Spine Hospital patients will be evaluated as to fall risk using the current fall risk assessment procedures employed by OSU Medical Center and administered in the usual and customary fashion upon evaluation on the floor and Pod.
 
Any patient fall is to be reported and evaluated following current processes and procedures developed by the OSU Brain and Spine Institute as maintained with IHIS.
 
If a fall risk patient is admitted to the unit and is not otherwise disqualified by the Study Exclusion Criteria, the patient and/or LAR in form of a Patient Consent document, will be given information about and the opportunity for the patient to participate in the Study. If the patient or legal surrogate declines participation, the patient will receive standard of care provided prior to the Study.
 
Upon receiving a consent to participate, the patient will be fitted with a monitored PUP™ sock sized to the patient's foot from the Study inventory, and thereafter enrolled by a caregiver in the Palarum Fall Prevention System using an Android application on the IRT. The Palarum Fall Prevention System and PUP™ sock thereafter monitor the patient's activity 24x7 throughout the patient's entire length of stay. During the patient's stay, the PUP™ sock will be evaluated daily for proper fit, patient comfort, and patient safety. Upon discharge or transfer, the patient is un-enrolled from the system again

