--	---

	
utilizing the IRT. All patient relevant fall data, including system performance, is collected and stored in the PCS for future study and evaluation. Any patient fall is to be reported and evaluated following current OSU Medical Center processes and procedures independent of the Palarum Fall Prevention System.
 
Technical support for the Palarum Fall Prevention system is available by phone at [name] [contact] and email, [contact], 24x7. If there is a Palarum Fall Prevention System outage each Intervention Group Pod should follow policies related to downtime procedures for fall risk patients.

CONTROL PRODUCT, DOSE AND ROUTE OF ADMINISTRATION	N/A
DURATION OF SUBJECT PARTICIPATION AND DURATION OF STUDY	Duration: Once a patient has been placed in the fall risk protocol, the patient will remain in the study until a nurse removes the patient from risk fall status or the participant has been discharged from the hospital.
CONCOMITANT MEDICATIONS	
Allowed: YES
 
Prohibited: NONE

EFFECTIVENESS EVALUATIONS	
Effectiveness evaluation data will be collected by the Palarum Fall Risk System, and incorporated and integrated with patient diagnosis, co-morbidities, and other medical data within REDCap including:
 
 1. Enrollment Data 
 a. Patient Identifier/MRN b. Patient Weight c. Patient Sock Size (S-M-L-XL) d. Sex e. Pod and Room/Bed f. Date g. Time h. Sock Number i. Sensor Number 2. Event Logs 3. Time of stand alert 4. Time to clear 5. Who cleared stand 6. Manual or Automatic termination 7. Accelerator and Gyroscopic Data surrounding each stand event

	8. Pressure on foot 9. Motion of patient
PRIMARY ENDPOINT	Fall rate per patient days within the study sample population
SECONDARY ENDPOINTS	
As collected by the Palarum Fall Prevention System, validated by manual audits of thereof, and integrated with REDCap,
 
 • Rate of false alerts • Rate of fall related patient safety events • Time to respond to alert • Pressure on foot • Motion of patient • Alert fatigue analyzed and measured by alert responded/alerts generated over time. • Notification system alerts only the closest five caregivers when a fall risk patient is up • Time to staff notification (latency) when a fall risk patient is up and unattended • Time to clear data • Identification of caregiver clearing alert • Determination of manual or automatic termination

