3 STUDY OBJECTIVES

3.1 Primary Objective

The primary objective of this study is to determine if the fall incidence rate for patients with the intervention, Palarum LLC's, PUP™ (Patient is Up) System is less than the historical incidence rate of patient falls in the units under study.

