## Palarum Data

### Primary dataset

- 732 entries with multiple enrollment and unenrollment dates (technical error)
- 569 patients after data cleaning multiple entries by limiting data to first enrollment and last unenrollment
- Variables included – floor, unit, enrollment date, unenrollment date. From these we calculated length of stay.

Variable	Level	Total (n=569)
OSU unit	Missing	3 (1%)
	10 East	127 (22%)
	10 South	108 (19%)
	8 East	64 (11%)
	8 South	102 (18%)
	9 East	81 (14%)
	9 South	84 (15%)
Length of Stay (Days)	Median [IQR] (min, max)	2 [1, 3.9] (0, 127.2)

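### The patient-day clock does not stop when PUP stops: Section 13.2 runs past transfer off the study units, and the SAP counts any un-enrolled gap, with no matching rule for falls

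*Protocol*

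**What the plan says.** Protocol Section 13.2 sets the denominator of the primary endpoint: "patient days are counted from the initiations of the PUP™ System until discharge or removal from the fall risk protocol". The synopsis (Primary Analysis Plan) gives the same rule. Transfer is not an end point in either place.

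The synopsis row on duration shows that discharge here means leaving the hospital, not the unit. Participation lasts "until a nurse removes the patient from risk fall status or the participant has been discharged from the hospital".

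The synopsis row on method of use stops the device earlier: "Upon discharge or transfer, the patient is un-enrolled from the system again".

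The comparator is tied to the units. The synopsis takes historical data "from nursing units where the intervention is being undertaken", and Section 3.1 asks whether the rate with PUP "is less than the historical incidence rate of patient falls in the units under study".

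For the numerator, the method-of-use row says: "Any patient fall is to be reported and evaluated following current OSU Medical Center processes and procedures independent of the Palarum Fall Prevention System". No passage limits the falls that count to time on the device or on the study units.

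The SAP works differently. Under Primary dataset, 732 entries became "569 patients after data cleaning multiple entries by limiting data to first enrollment and last unenrollment", and length of stay was calculated from those two dates. Under Secondary dataset, falls for the primary outcome come from the Palarum event file (4,999 stands, 0 falls).

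**The concern.** A fall-risk patient who moves from one of the six pods to another part of the hospital loses PUP but, under Section 13.2, keeps accruing PUP patient-days. Those days are not exposed to the device and are not comparable with a benchmark from the study units. In a single-arm trial tested against a fixed rate of 0.004, the patient-day total is half of the only estimate, and no control group carries the same error.

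The effect depends on the numerator. If falls after transfer are not counted, the off-unit days dilute the rate, and a device with no effect is more likely to pass. If they are counted, PUP is charged with falls on units where it was not in use. The protocol does not say which applies.

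The SAP's rule removes the tail after the last unenrollment but not the gaps before it. Any period when a patient was un-enrolled and later re-enrolled counts as exposure. The Palarum event file is not shown to capture falls in such a period.

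**Working it through.** **1. The clocks side by side**

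| Quantity | Where | Ends at, or covers |
|---|---|---|
| PUP monitoring | Protocol synopsis, method of use | Discharge or transfer |
| Participation | Protocol synopsis, duration | Loss of fall-risk status or hospital discharge |
| Patient-days, protocol | Protocol synopsis and 13.2 | Discharge or loss of fall-risk status |
| Benchmark | Protocol synopsis, primary objective; 3.1 | The study units |
| Falls, protocol | Protocol synopsis, method of use | Hospital reporting, no limit by time or unit |
| Length of stay, SAP | SAP, Primary dataset | First enrollment to last unenrollment, gaps included |
| Falls, SAP | SAP, Secondary dataset | Palarum event file |

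The protocol's patient-day rule outlasts the device whenever a patient who is still a fall risk leaves the pods.

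**2. Direction of the bias**

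Let f be the share of counted days that are off-unit, and r the rate of counted falls per 1000 of those days. With no device effect, the expected rate per 1000 is 4(1 − f) + f·r.
- r = 0 (off-unit falls not counted): 3.8 at f = 5%, 3.6 at 10%, 3.2 at 20%.
- r = 4: no bias.
- r above 4: the rate is too high, against the device.

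**3. The plan's own figures first**

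- *Sample size (13.4).* The section claims at least 70% power for a 25% reduction from 0.004, at one-sided alpha 0.1, with 2360; it gives no unit and no stay per patient. The exact Poisson test first reaches 70% at 11,800 days, and 11,800 / 2360 = 5.0 days per patient. Null mean: 0.004 × 11,800 = 47.2. The largest count with P(X ≤ c) at or below 0.1 is c = 38, where P = 0.0997. Alternative mean: 0.003 × 11,800 = 35.4, with P(X ≤ 38) = 0.706. So 11,800 days reproduces the claim, but the 5 days is an inference.
- *SAP bound.* With 0 falls in 2211.6 days, the one-sided 90% upper bound is −ln(0.1) / 2211.6 = 2.3026 / 2211.6 = 1.041 per 1000 days. This matches the SAP's 1.04.

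**4. Planned design, off-unit falls not counted, no device effect**

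The success threshold stays at 38 falls and the mean becomes 47.2(1 − f).

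| f (assumed) | Mean | P(X ≤ 38) |
|---|---|---|
| 0 | 47.20 | 0.0997 |
| 5% | 44.84 | 0.172 |
| 10% | 42.48 | 0.276 |
| 20% | 37.76 | 0.558 |

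The pattern does not hang on 11,800. At 12,050 days (the two-variance normal formula) the threshold is also 38, and the error goes from 0.077 to 0.139 at 5% and 0.233 at 10%.

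**5. SAP data, a share f of the 2211.6 days removed**

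Bound = 2.3026 / [2211.6(1 − f)].

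| f (assumed) | Days left | Upper bound per 1000 |
|---|---|---|
| 0 | 2211.6 | 1.04 |
| 5% | 2101.0 | 1.10 |
| 10% | 1990.4 | 1.16 |
| 20% | 1769.3 | 1.30 |

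The bound reaches 4 per 1000 only when 2.3026 / 0.004 = 575.6 days are left, that is, after removing 1 − 575.6 / 2211.6 = 74% of the days. The longest stay, 127.2 days, is 5.8% of the total. Without it the bound is 2.3026 / 2084.4 = 1.10. The SAP does not say whether that stay contains a gap.

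**The case against.** The best defence is that Section 13 of the protocol leaves modifications to the SAP, and the SAP did not count to hospital discharge. It stopped at the last unenrollment. Since patients are un-enrolled at transfer, days after a final transfer are not in the 2211.6. That stands. A reader might infer from Section 13.2 that the reported denominator is swollen by post-transfer days; the SAP does not support this. Gaps between enrollments remain, but the SAP attributes the multiple entries to technical error and gives no gap lengths. They may be few and short.

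A second defence is about direction. A reader might infer that the rule necessarily lowers the fall rate. The documents do not support that either. The protocol keeps the patient in the study and sends every fall through hospital reporting, so days and falls could run over the same period. Equal off-unit rates would then give no bias, and higher ones would work against PUP.

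Third, the sizes are hypothetical. Neither the 11,800 days nor any off-unit share is in the documents. Transfer is also undefined: enrollment runs through an in-room tablet, so some un-enrolments may be moves between study rooms or pods. This limits what can be said about size.

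None of this reconciles the protocol's rules, makes un-enrolled gaps count as exposure to PUP, or says which falls belong with which days.

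**Conclusion.** The point holds as an inconsistency in the end of exposure, with no matching rule for falls. Read literally, the protocol lets days off the study units and off PUP into the denominator. The SAP closes most of that route but leaves un-enrolled gaps in.

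For the planned design, the type I error could rise from 0.10 to 0.17 or 0.28. This rests on three assumptions: 11,800 days, an off-unit share of 5% or 10%, and no off-unit falls counted. It illustrates sensitivity and does not estimate what happened.

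A reader might go further and infer that the SAP's finding of a rate below 4 per 1000 is unsafe on this account. It is not. With 0 falls the point estimate cannot be lowered, and the bound stays far below 4 for any plausible share of days removed. That holds for the denominator only: if hospital reports showed falls in the same window that the Palarum file lacks, the estimate itself would change, and the documents do not settle this. The repair is cheap and removes an avoidable bias, so it should be made.

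**What to change.** Reconcile the synopsis rows on method of use, duration and primary analysis, Section 13.2, and the SAP's Primary dataset rule. This concerns what the analysis counts, not when the sock is worn.

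- **One window for days and falls.** Count time on any of the six study pods from PUP initiation to the earliest of discharge, removal of fall-risk status, transfer off the study pods, or withdrawal from the study. Restart on return and re-enrolment. Moves between study pods do not stop the clock.
- **Early discontinuation on a pod.** Section 11.1 lists refusal or intermittent wearing of the sock as reasons to discontinue. State how later days and falls on the pod are handled, and run a sensitivity analysis the other way.
- **SAP denominator.** Sum the separate enrollment intervals, or add a sensitivity analysis that excludes the gaps between them.
- **SAP numerator.** Count falls from hospital fall reports over the same window, in line with the protocol's reporting rule.

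The wording change is short. The cost is slightly fewer patient-days and some data work: the enrollment log must be cleaned of its multiple entries, or a transfer extract obtained, because the SAP found the unit, department and room fields in the admission data not useful.

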4 STUDY DESIGN

4.1 Study Overview

- **Problem** - Falls occur at a rate of 5.5 per 1000 patient days in US hospitals. In addition to the human morbidity and mortality costs, falls cost hospitals in excess of \$8 billion in unreimbursed charges. No intervention to date has been shown to significantly reduce that rate.
- **Purpose** - To determine the effectiveness, if any, of the PUP™ Fall Prevention System. The hypothesis is that the System will reduce the fall rate by at least 25% of prior years' average fall rate.
- **Population to be studied** - All fall risk patients, eighteen years old or older, admitted to OSU Brain and Spine Hospital on Floors 8, 9, and 10 until the sample size is reached.
- **Research Design** – Single arm trial
- **Extent of Researcher Interference** - Minimal, only studying events as they normally occur. The PUP™ System will have been previously evaluated and approved for use as the standard of care at the OSU Medical Center Brain and Spine Hospital in accordance with the terms of an agreement between Palarum and OSU Medical Center dated March 28, 2018.
- **Time horizon** - Current.
- **Study setting** - Non-contrived. OSU Medical Center Brain and Spine Hospital.
- **Measurement and measures**
 - Patient fall rate (measured as number of falls/1000 patient days) data collection and reporting forms, criteria and protocols for the three calendar years preceding initiation of the research.
 - Patient fall rate data collection and reporting forms, criteria, and protocols for the research period calendar year.
 - Data collection standards and protocol for/of;
 - Positive stand detection alert
 - Negative stand detection alert
 - Participant inclusion, exclusion or exemption
 - Sampling methods of 1-3 above
 - Report form(s), structure and content
 - Participant or data exclusion standards, if any.
- **Data Collection Method** - Unobtrusive automated physical measurement using the PUP™ sock, sensors, wireless technology, and REDCap.

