6.2 Inclusion Criteria

- Written informed consent obtained from subject (and/or LAR) and ability for subject to comply with the requirements of the study.
- All fall risk patients, eighteen years old and older, on Floors 8, 9 and 10 of the OSUWMC Brain and Spine Hospital, with “fall risk” as defined by OSU criteria, for whom no medical condition prohibits their participation in the program, (see Exclusion Criteria).

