6.3 Exclusion Criteria

- Presence of a condition or abnormality that in the opinion of the Investigator would compromise the safety of the patient or the quality of the data.
- Patients whose medical condition prohibits their participation in the program, which would include among others, patients with an anatomy or wound issue on their feet or around their calves that would bar them from wearing socks on either foot, and/or patients for whom the sock would impede medical treatment.

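### The SAP takes its zero fall count from the Palarum stand-event dataset rather than hospital fall reports, and the benchmark of 0.004 is given without counts or population

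*Protocol*

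**What the plan says.** **Test.** Protocol section 13.2: "we will test whether the observed fall rate is less than the historical rate of 0.004". It is a one-sided one-sample Poisson test at alpha 0.1, reported with a one-sided 90% upper bound. Patient-days run from the start of the system "until discharge or removal from the fall risk protocol".

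**Endpoint.** Section 5.1 counts any unplanned descent to the floor, injured or not. It explicitly includes assisted falls and rolling off a low bed onto a mat.

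**Where falls are recorded.** The synopsis (Method of Use) says twice that a fall is reported and evaluated through the hospital's existing process. One statement places this in IHIS, and the other says that it is independent of the Palarum system. The same section says that relevant fall data are stored in the Palarum cloud. The synopsis entry on effectiveness evaluations has effectiveness data collected by the Palarum system.

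**What was counted.** The SAP (Palarum Data, Secondary dataset) lists 4,999 stands and 0 falls, and states that this dataset supplied the falls for the primary outcome. Under Ohio State Data, the only falls variable is history of falling.

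**Benchmark.** The synopsis and the SAP objective compare the rate with the study units, "when compared to historical NDNQI data for the prior 12 months" in the synopsis wording. Section 3.1 asks whether the rate "is less than the historical incidence rate of patient falls in the units under study". Section 4.1 says "The hypothesis is that the System will reduce the fall rate by at least 25% of prior years" and goes on to refer to their average. The study population is narrower than the units: fall-risk adults who consent (or whose representative does), with "ability for subject to comply with the requirements of the study", and without a foot or calf problem that "would bar them from wearing socks on either foot".

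**The concern.** The primary result is a count of zero, so it is only as good as the source that could have recorded a fall. The protocol describes the device as detecting pressure, standing and stepping (synopsis; sections 1 and 4.2). The event-log items that it lists concern stands and alerts. A roll onto a floor mat need not involve a stand, and an assisted fall happens with a caregiver present, when the system is designed not to alert or to clear its alert. Neither document says how a fall would enter the Palarum dataset. Safety reporting is no clear backstop, because section 5.3 says that falls are not adverse events arising from the system.

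If the benchmark falls came from hospital reporting and the study falls from device events, the study rate could be lower with no device effect. At stake are both the significance of the test and the upper bound of 1.04 per 1000 days.

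A second, smaller matter is that no section gives the falls or patient-days behind 0.004, or says whether it covers all unit patients or only those at fall risk.

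**Working it through.** **Inputs.** Null rate 0.004 per patient-day, one-sided alpha 0.1 (protocol section 13.2). 0 falls, T = 2,211.6 days, upper bound 1.04 per 1000 (SAP, Study Objectives). Patient counts 569, 585 and 521, with 48 and 58 unmatched (SAP). Benchmark days are not given, so B is an assumed range.

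**1. Reproduce the SAP's bound.** With 0 falls the bound is -ln(0.1)/T = 2.3026/2,211.6 = 1.041 per 1000, which matches 1.04. The SAP gives no p-value; it is exp(-0.004 × 2,211.6) = exp(-8.846) = 0.00014.

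**2. Vary the fall count.** Expected falls at the benchmark are 0.004 × 2,211.6 = 8.85. For x falls, p = P(X ≤ x) with X ~ Poisson(8.846). The upper bound is the 0.90 quantile of a gamma distribution with shape x + 1, divided by T.

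| Falls in 2,211.6 days | p against 0.004 | Upper 90% bound per 1000 |
|---|---|---|
| 0 | 0.00014 | 1.04 |
| 1 | 0.0014 | 1.76 |
| 2 | 0.0070 | 2.41 |
| 3 | 0.024 | 3.02 |
| 4 | 0.060 | 3.61 |
| 5 | 0.125 | 4.19 |

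Significance is lost at 5 falls, which is fewer than the 8.85 expected with no effect. The upper bound in each row is also the lowest fixed benchmark that the count would beat.

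**3. Vary the fixed benchmark, with 0 falls.** p = exp(-benchmark × T). For 1 / 2 / 3 / 4 / 5 per 1000 it is 0.110 / 0.012 / 0.0013 / 0.00014 / 0.00002. The conclusion holds for any fixed benchmark above 1.04.

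**4. Allow for benchmark sampling error.** Set benchmark falls y = 0.004B. The exact conditional test is p = P(X ≤ x) with X ~ Binomial(x + y, T/(T + B)).

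- 0 falls: p = 0.0018 at an assumed B = 2,500, 0.00034 at 10,000 and 0.00016 at 120,000. The conclusion does not change.
- 4 falls: 0.080 to 0.062 over B = 10,000 to 120,000, but 0.133 at B = 2,500.
- 5 falls: 0.151 to 0.128 over B = 10,000 to 120,000.

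**5. Design-stage alpha.** If 0.004 is itself an estimate from B days, the actual alpha depends on B and on study exposure, and the protocol gives neither. At an assumed 11,800 study days (2360 × an assumed 5-day stay) it runs from 0.172 (B = 10,000) to 0.096 (B = 120,000). At the SAP's mean stay, 2,211.6/569 = 3.89 days (2360 × 3.89 ≈ 9,173 days), it runs from 0.154 to 0.093. At the 2,211.6 days analysed it is 0.106 for B = 5,000 and below 0.1 from B = 10,000 upward.

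**6. Linkage.** 569 - 521 = 48 agrees with the SAP's count of Palarum patients missing from the hospital data. 585 - 521 = 64 does not agree with the 58 stated for the other direction. Hospital falls cannot be attached to the 48 until this is resolved.

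**The case against.** The protocol names both routes. It stores fall data in the Palarum cloud and has effectiveness data collected by the system, so using the Palarum dataset is not plainly a departure. The SAP does not say how falls entered that dataset, and staff may have entered hospital-reported falls there. This stands as a limit: the source is ambiguous, not proven wrong. It does not remove the problem, because hospital reporting is stated to be independent of the system and the SAP lists no in-study hospital fall reports.

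A one-sample test against a prespecified rate is a standard single-arm choice, stated consistently in the protocol. That also stands. A reader might infer that treating 0.004 as known seriously inflates the error rate of this trial. The documents do not support that as a headline: the larger alphas need small assumed benchmark exposures and an assumed length of stay, and the reported p-value barely moves.

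A reader might also infer that the benchmark was computed over three years, because section 4.1 mentions "protocols for the three calendar years preceding initiation of the research". That item concerns fall-rate data collection and reporting forms, criteria and protocols; it does not say that 0.004 comes from that period. Only the prior-years average in the hypothesis clearly differs from the 12-month window.

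**Conclusion.** The concern holds, with the fall source as its main part. The documents do not establish that zero falls in the Palarum dataset means zero falls under the section 5.1 definition. The result tolerates up to 4 hospital-reported falls and fails at 5, taking 0.004 as fixed and 2,211.6 days as correct. The upper bound of 1.04 does not depend on the benchmark, but it does depend on the fall count.

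A reader might infer that falls were missed. The documents do not show that; they show only that the hospital source was not reported.

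The benchmark gap is secondary. If 0.004 covers all unit patients, restriction to fall-risk patients would be expected to raise the untreated rate and make the test conservative. Selection by consent and ability to comply could move it either way. The missing counts do not overturn the conclusion at 0 falls. Confidence is medium, because the route by which falls reached the Palarum dataset is not described.

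**What to change.** 1. Resolve the patient linkage first: the 48 Palarum patients without hospital data, and the 58 against 64 in the other direction.
2. Extract hospital fall reports for the enrolled patients over the same patient-days. Rerun the planned one-sample test and upper bound on that count, report it beside the Palarum count, and say how falls enter the Palarum dataset.
3. State the falls, patient-days and population behind 0.004, and reconcile the 12-month window with the prior-years average.
4. Add two analyses, labelled as sensitivity analyses chosen after the result was known: the conclusion over benchmark rates of 1 to 5 per 1000 and, if benchmark counts are available, an exact two-sample Poisson rate ratio using hospital-reported falls on both sides.

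The cost is one hospital data extract and a short SAP addition; the planned test stays primary. The result may become less favourable. Selection by consent and the lack of a concurrent control remain, so a lower rate still could not be attributed to the device alone.
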